The primary outcome variable will be the change in number of Content Units (CU) in picture description from baseline to 1-week post-treatment. Hypothesis 1A is: Participants will show greater improvement in CU from baseline to 1-week post treatment, during the EEG neurofeedback condition than during the sham condition.

To test Hypothesis 1A, we will subtract baseline CU from 1-week post-treatment CU, for each condition. We will use a paired t-test to determine if, as a group, patients showed greater increase in CU during the neurofeedback condition compared to the sham condition. We will also carry out paired t-tests for post-stroke aphasia and PPA separately, to determine if the effect was greater in one group.

b. Secondary outcome variables

Hypothesis 1B-F take the form of: Participants will show greater improvement in [outcome variable] from baseline to 1-week post treatment, during the EEG neurofeedback condition than during the sham condition.

To test each hypothesis 1B-F, we will subtract baseline score from follow up scores (1-week post-treatment), for each condition. We will use paired t-tests to determine if, as a group, patients showed greater improvement during the neurofeedback condition compared to the sham condition, at each follow-up. We will correct for multiple comparisons using a Bonferroni correction.

Hypothesis 2A is: We will be able to identify baseline characteristics (demographics and baseline severity measures, as well as qEEG abnormalities) that influence change in the primary outcome measure (change in CU in picture description from baseline to 1-week post-treatment).

To test this hypothesis, we will carry out multivariable linear regression, with the dependent variable (change in CU in picture description from baseline to 1-week post-treatment), and independent variables of age, baseline CU, baseline OANB, baseline COWA, baseline sleep quality, baseline S-anxiety (STAI), brainwave activity (absolute power, peak amplitude frequency) in each frequency band (alpha, beta, theta, delta, gamma) on qEEG.

Hypothesis 2B is: We will be able to identify changes in secondary outcome measures and changes in qEEG that correlate with the primary outcome measure (change in CU from baseline to 1-week post-treatment). These results will allow us to identify variables to explore the mechanisms of the effects.

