To test this hypothesis, we will carry out Pearson correlations between the dependent variable (change in CU in picture description from baseline to 1-week post-treatment), and change in CU, change in OANB, change in COWA, change in absolute power and peak amplitude frequency within each frequency band (alpha, beta, theta, delta, gamma) on qEEG, change in coherence on qEEG (e.g., coherence between left and right hemispheres).

Hypothesis 3A is: Greater improvement in qEEG normalization toward healthy control group (e.g. alpha enhancement with absolute power and peak amplitude frequency ≤ 1.5 standard deviations away from healthy group average) will be observed in the EEG neurofeedback training condition compared to sham training condition.

Date: November 11, 2021
Principal Investigator: [name]
Application Number: IRB00242136
NCT# NCT04290988
Study Title: Circuitry Assessment and Reinforcement Training Effects on Recovery (CARTER)

To test this hypothesis, we will compare baseline and follow-up z-scores for absolute power and peak amplitude frequency of each of the frequency bands (alpha, beta, theta, delta, gamma) by subtracting the absolute value baseline z-score from the absolute value follow-up z-scores for each condition. We will use paired t-tests to determine if, as a group, patients showed greater improvement during the neurofeedback condition compared to the sham condition, at each follow-up. We will correct for multiple comparisons using a Bonferroni correction. We will also carry out paired t-tests for post-stroke aphasia and PPA separately, to determine if the effect was greater in one group.

Hypothesis 3B is: Greater connectivity within the attentional network and the language network (and right hemisphere homologues) will be observed in the EEG neurofeedback training condition compared to sham training condition.

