To test this hypothesis, we will compare baseline and follow-up z-scores for coherence in each of the frequency bands (alpha, beta, theta, delta, gamma) by subtracting the absolute value baseline z-score from the absolute value follow-up z-scores for coherence in each condition. We will use paired t-tests to determine if, as a group, patients showed greater improvement during the neurofeedback condition compared to the sham condition, at each follow-up. We will correct for multiple comparisons using a Bonferroni correction. We will also carry out paired t-tests for post-stroke aphasia and PPA separately, to determine if the effect was greater in one group.

c. Statistical plan including sample size justification and interim data analysis

Statistical Analyses

Statistical tests to evaluate each hypothesis are described above. No interim data analyses are planned, although we will become unmasked to condition after each participant completes the 5 week follow-up

Sample Size Determination

This study is a novel application of neurofeedback for treatment of aphasia, and we have no preliminary data to guide a power analysis. However, we will use this preliminary cross-over study (with each patient as their own control) to identify effect size (if any), in order to plan a randomized, double-blind, parallel, sham-controlled trial. For this preliminary trial, we plan to study 8 patients per year with post-stroke aphasia, and 8 patients per year with PPA, based on our other ongoing trials of post-stroke aphasia and PPA, in which we have found that it is feasible to recruit and retain 8-10 of each per year. We hope to obtain a total of 40 patients with post-stroke aphasia and 40 with PPA over 5 years, to obtain preliminary data for a multicenter, randomized, double-blind, parallel, sham-controlled trial, if the preliminary results are positive.

Missing Data

We plan to minimize missing data by avoiding prolonged intervals between conditions. Most of the study will take place within 7-11 weeks, with each person scheduled to have a 5 week follow up to determine if any changes are long-lasting. To minimize biases, analyses will be by

Date: November 11, 2021
Principal Investigator: [name]
Application Number: IRB00242136
NCT# NCT04290988
Study Title: Circuitry Assessment and Reinforcement Training Effects on Recovery (CARTER)

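### Hypothesis 2B correlates change scores with no diagnosis term in a mixed stroke and PPA sample, so a stroke–PPA difference in mean change on both measures produces a correlation by itself

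*Combined protocol and SAP*

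**What the plan says.** Section 7b states Hypothesis 2B as follows: "We will be able to identify changes in secondary outcome measures and changes in qEEG that correlate with the primary outcome measure". The method is "Pearson correlations between the dependent variable (change in CU in picture description from baseline to 1-week post-treatment), and change in CU, change in OANB", and the list goes on to "change in COWA, change in absolute power and peak amplitude frequency within each frequency band (alpha, beta, theta, delta, gamma) on qEEG" and to change in coherence. The use of the results is also stated: "These results will allow us to identify variables to explore the mechanisms of the effects".

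No covariate, stratum or partial correlation is named for 2B. For Hypothesis 1A the same section adds: "We will also carry out paired t-tests for post-stroke aphasia and PPA separately, to determine if the effect was greater in one group". Hypotheses 3A and 3B carry the same sentence; 2B has no counterpart. The independent variables listed for the 2A regression do not include diagnosis either. Section 7c refers back to 7b for the tests of each hypothesis, so nothing there supplies the missing term.

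On the sample, section 7c says "we plan to study 8 patients per year with post-stroke aphasia, and 8 patients per year with PPA" and "We hope to obtain a total of 40 patients with post-stroke aphasia and 40 with PPA over 5 years". Section 2 labels the secondary objective, to which 2B belongs, exploratory.

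**The concern.** A simple correlation over a sample made of two groups mixes two things: how the measures move together within each group, and how far apart the group means lie. The sample here joins aphasia after stroke with a progressive disease. The plan itself allows that response may differ between them, since it tests 1A, 3A and 3B by diagnosis for that reason. If mean change in CU differs by diagnosis, any OANB, COWA or qEEG change whose mean also differs by diagnosis acquires a correlation with CU change, whether or not the two are linked in individual participants. Several correlates can be affected at once. If the two differences have opposite signs, the between-diagnosis part is negative and can hide a real positive link within diagnosis.

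What is at stake is the choice of variables. 2B is the step that decides which measures are taken forward as candidates for mechanism, and a variable could be chosen because it separates stroke from PPA and for no other reason.

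Separately, the list sets change in CU against itself. That correlation is 1 by definition and carries no information.

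**Working it through.** **Inputs from the documents.** Section 7c plans 8 per year per diagnosis over 5 years: 8 × 5 = 40 per diagnosis and 2 × 40 = 80 in total. This reproduces the plan's figures. The share of each diagnosis is p = 0.5, so p(1−p) = 0.25. For a given pair of differences this equal split gives the largest pooled r.

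**Inputs assumed.** The documents give no stroke–PPA difference in mean change on any measure and no significance level for 2B. I take differences d1 and d2 in units of the within-diagnosis SD, equal SDs in the two diagnoses, zero correlation within each diagnosis, and a nominal two-sided 0.05 test.

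**Expected pooled correlation.** The between-diagnosis covariance is p(1−p)·d1·d2, and each variance is 1 + p(1−p)·d². Hence

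r = 0.25·d1·d2 / √[(1 + 0.25·d1²)(1 + 0.25·d2²)],

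which for d1 = d2 = d is 0.25d² / (1 + 0.25d²).

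- d = 0.3: 0.0225/1.0225 = 0.022
- d = 0.5: 0.0625/1.0625 = 0.059
- d = 0.8: 0.16/1.16 = 0.138
- d = 1.0: 0.25/1.25 = 0.200
- d1 = 0.5, d2 = 1.0: 0.125/√(1.0625 × 1.25) = 0.108
- d1 = 0, any d2: 0

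**Threshold.** With n = 80, t on 78 degrees of freedom is 1.991, and the critical |r| is 1.991/√(78 + 1.991²) = 0.220.

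**False-positive rates.** These come from 40,000 simulated trials of 40 + 40 per scenario, normal data, no within-diagnosis link. The adjusted column is the partial correlation given diagnosis, on 80 − 3 = 77 degrees of freedom.

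| Difference in mean change (SD) | Expected pooled r | Pooled test rejects | Adjusted test rejects |
|---|---|---|---|
| 0 and 0 | 0.00 | 4.9% | 4.9% |
| 0 and 1.0 | 0.00 | 4.9% | 5.0% |
| 0.2 and 0.2 | 0.01 | 5.1% | 5.1% |
| 0.3 and 0.3 | 0.02 | 5.6% | 5.0% |
| 0.5 and 0.5 | 0.06 | 7.9% | 5.0% |
| 0.5 and 1.0 | 0.11 | 16.1% | 4.8% |
| 0.8 and 0.8 | 0.14 | 23.1% | 5.0% |
| 1.0 and 1.0 | 0.20 | 44.3% | 5.0% |

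The Monte Carlo standard error is at most √(0.443 × 0.557/40,000) = 0.25 percentage points. Adjustment holds the rate at 4.8% to 5.1% in every row.

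**The case against.** The strongest case against has five parts.

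- **The size is unknown.** No figure in the documents supports a gap of 0.8 or 1 SD, and section 7c says there are no preliminary data to guide a power analysis. At 0.3 SD or less the effect is negligible. This stands: the table is a range, not a forecast.
- **The change score is not pinned down.** 2B does not say whether it uses the active period, the sham period, both, or active minus sham. For active minus sham, a difference in course common to both periods largely cancels, and the artefact then needs a different treatment response by diagnosis. This stands as a limit on size. It does not remove the problem, because the plan leaves the single-period reading open and treats different response by diagnosis as possible.
- **The aim is exploratory.** No efficacy result depends on 2B. This limits the consequence, but choosing variables is exactly the use that the artefact would distort.
- **Between-diagnosis variation may be signal.** If treatment moves both qEEG and CU more in one diagnosis, adjustment removes that. This stands, and is why the pooled correlation should be kept for description.
- **Adjustment does not make the screen a 5% procedure.** With change in CU removed, the list holds OANB, COWA, 5 bands × 2 qEEG measures and coherence. Counting coherence once, that is 1 + 1 + 10 + 1 = 13 correlates. No correction is stated for 2B, so if the tests were independent the chance of at least one false positive at 0.05 would be 1 − 0.95^13 = 49%. This is true, but it is a separate matter.

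A reader might infer that any two measures on which stroke and PPA differ will correlate. The documents and the arithmetic do not support that: the difference must be in mean change, not baseline level, and must be present on both measures. A reader might also infer that the self-correlation undermines 2B. It looks like a drafting slip. The list also omits the sleep, anxiety and sleep-medication changes that section 2 names as secondary outcomes, but the documents do not say whether one of those was intended.

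**Conclusion.** The point holds as a conditional one. Pooling is inferred from the absence of any diagnosis term or stratum in 2B, set against its presence in 1A, 3A and 3B; the plan does not use the word. Given pooling, a stroke–PPA difference in mean change on both measures yields a non-zero correlation with no within-diagnosis link. The inflation is negligible up to about 0.3 SD on both, small at 0.5 SD (8%), material from about 0.8 SD (23%) and large at 1 SD (44%). It is absent when only one measure differs. The differences, the equal within-diagnosis SDs and the 0.05 level are assumptions.

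A reader might go further and conclude that 2B will produce false mechanisms of neurofeedback. The text does not support that: the results are used only to pick variables to explore, and the size of any artefact in this trial is unknown. Nor would adjustment for diagnosis by itself turn a correlation into a mechanism. The confidence is in the direction and cause of the bias, not in its size. The change is worth making because it is cheap and the plan has no data to rule out the larger differences.

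**What to change.** In section 7b, under Hypothesis 2B, state that variables will be chosen on partial correlations with change in CU adjusted for diagnosis (stroke or PPA). Report the two within-diagnosis correlations beside each, and keep the pooled Pearson correlation as descriptive only. Remove change in CU from the list of correlates.

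The cost is one degree of freedom per correlation. At 80 participants the critical |r| moves from 0.220 to 1.991/√(77 + 1.991²) = 0.221. Any real between-diagnosis signal is then seen only in the pooled figure. The within-diagnosis correlations rest on 40 participants each, so they are imprecise: with t on 38 degrees of freedom of 2.024, the critical |r| is 2.024/√(38 + 2.024²) = 0.312. They serve to show whether the two diagnoses agree, not to select variables. No new data, visits or participants are needed.

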Since EEG biofeedback targets the underlying brainwave patterns (e.g., quantity and amplitude of waves in various frequency bands) that ultimately affect and influence an individual’s behavior, the resultant behavioral outcomes can vary greatly in response to this intervention. For instance, when targeting an increase of ideal brainwave patterns and a reduction of deviant patterns (e.g., reducing the amount of excess waves in a given frequency band), one could see improvements in a variety of neuropsychological domains such as attention (Egner & Gruzelier, 2004; Fuchs, Birbaumer, Lutzenberger, Gruzelier, & Kaiser, 2003; Yan et al., 2008), memory (Escolano, Aguilar, & Minguez, 2011; Klimesch, 1999), mood (Wang et al., 2019), language skills (Mroczkowska, Bialkowska, & Rakowska, 2014; Nan, Dias, & Rosa, 2019), and anxiety (Banerjee & Argáez, 2018; Moore, 2000). Also, since z-score neurofeedback training targets deviant brainwave activity across multiple frequency bands, behavioral outcomes can vary across individual participants depending on the brainwave patterns that the individual’s brain adopts in response to the neurofeedback training. For instance, one individual may experience an increase in alpha wave presence, which is usually associated with a relaxed mental state and report a reduction in anxiety (Evans & Abarbanel, 1999). Whereas another individual may experience more normalization of beta-range brainwaves, which are associated with stronger focused attention (Marzbani, Marateb, & Mansourian, 2016). Since it is not the behavior that is directly targeted, but the underlying brainwave patterns, the resultant behavioral effects of this treatment can vary across individuals.

For this reason and because this intervention can impact general cognitive skills (not necessarily skills specific to speech and language functioning), we would like to add behavioral speech-language therapy to target language skills in a more direct way and examine if EEG biofeedback may augment speech-language therapy for individuals with post-stroke aphasia and Primary Progressive Aphasia (PPA) by improving neural connectivity through reinforcement of ideal brainwave patterns. We hypothesize that individuals who receive active EEG biofeedback in addition to behavioral (traditional) speech-language therapy will make greater gains in language outcomes when compared to individuals with receive sham EEG biofeedback training in addition to traditional speech-language therapy.

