Visit 1: Screening and Baseline Behavioral Assessment. These sessions involve language testing with the OANB (first), picture description, and COWA. This will be the baseline language testing for the first intervention period. Participants with an OANB score that exceeds an average of 80% accuracy will be excluded to leave at least a 20% improvement margin. That is, participants who already score close to ceiling may have limited room for naming improvement. During the first visit, participants will undergo screening assessments. This will determine if they are a candidate for the treatment. If the participant passes the initial screening portion, informed consent will be obtained.

Visit 2: Baseline qEEG and fNIRS. Participants will undergo qEEG brain mapping assessment to obtain baseline EEG analysis to assess brainwave patterns and to identify areas of abnormality compared to normative database of same-age healthy peer group to establish appropriate training goals for neurofeedback sessions. Participants will also undergo fNIRS assessments.

Visit 3-17: Intervention Phase I. These sessions will include the treatment sessions for the first intervention period. Prior to the start of treatment, participants will be randomly assigned to receive either “neurofeedback then sham” or “sham then neurofeedback.” For example, if a participant is randomly assigned to receive “neurofeedback then sham,” the first intervention period of 15 sessions will be neurofeedback training and the second intervention period will be 15 sessions of sham training. Participants will undergo treatment sessions within each intervention phase at a frequency of 2-5 sessions per week as their schedule allows. At each visit within this intervention phase, participants will also receive speech-language therapy (VNeST).

Date: November 11, 2021
Principal Investigator: [name]
Application Number: IRB00242136
NCT# NCT04290988
Study Title: Circuitry Assessment and Reinforcement Training Effects on Recovery (CARTER)

Visits will take approximately 45-minutes for EEG biofeedback training plus an additional 45-minutes for speech-language therapy.

Visit 18: 1-week Post-Intervention Assessment (following Intervention Phase I). This visit will involve post-treatment language testing, qEEG and fNIRS.

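### Hypothesis 3A (exploratory) averages every qEEG band over every participant although training goals are individual, so the plan lacks a test of whether training moved its own targets

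*Combined protocol and SAP*

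**What the plan says.** **How goals are set.** In Section 4a, Visit 2, the qEEG is done "to identify areas of abnormality compared to normative database of same-age healthy peer group to establish appropriate training goals for neurofeedback sessions". Section 3 (Background) adds that "z-score neurofeedback training targets deviant brainwave activity across multiple frequency bands", and gives the example of one person gaining alpha while another normalises in the beta range.

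**What is tested.** In Section 7b, Hypothesis 3A, "we will compare baseline and follow-up z-scores for absolute power and peak amplitude frequency of each of the frequency bands". The bands are alpha, beta, theta, delta and gamma. Change is formed "by subtracting the absolute value baseline z-score from the absolute value follow-up z-scores for each condition". Then: "We will use paired t-tests to determine if, as a group, patients showed greater improvement during the neurofeedback condition compared to the sham condition". A Bonferroni correction is promised without stating the number of tests. The tests are repeated in post-stroke aphasia and PPA separately. Nothing restricts, weights or stratifies by whether a feature was abnormal at Visit 2 or was a training goal.

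**The 1.5 SD figure.** The hypothesis illustrates normalisation with "peak amplitude frequency ≤ 1.5 standard deviations away from healthy group average". The figure is not used in the test.

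**Status and setting.** Section 2 places 3A under the Tertiary Objective and calls it exploratory. Section 5 requires no qEEG abnormality for entry. Section 7c hopes for 40 participants per diagnosis and says there are no preliminary data for a power calculation.

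**The concern.** What is trained can differ between participants, but what is tested does not. Absolute z-score has a floor at zero, so a participant already close to the norm in a band has almost nothing to gain there. Averaging such participants with those in whom the band was abnormal and trained pulls the active-minus-sham difference toward zero.

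3A is the direct check that active training normalised power and peak frequency. No other analysis supplies a targeted version. Hypotheses 2A and 2B relate qEEG to change in Content Units (CU), and the 3B coherence tests have the same all-participant form. If the CU result is null, the investigators will want to know whether training failed to shift the EEG or shifted it without helping language. A diluted 3A answers that poorly.

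**Working it through.** The documents give no power, effect size or alpha for 3A, so there is no figure to reproduce.

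**Inputs from the plan**
- N = 40 + 40 = 80 (accrual target, Section 7c).
- Features: 5 bands × 2 measures = 10 (Section 7b).

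**Assumptions**
- Bonferroni over ten tests: 0.05/10 = 0.005, two-sided.
- p: share of participants in whom a given feature was a target.
- d: effect in those participants, in SDs of the paired active-minus-sham difference; zero in the rest.

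**Dilution.** The whole-group standardised effect is p·d / √(1 + p(1−p)d²). With d = 0.5:
- p = 0.75: 0.375/√1.0469 = 0.367
- p = 0.50: 0.25/√1.0625 = 0.243
- p = 0.25: 0.125/√1.0469 = 0.122

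**Power for one named feature** (paired t, noncentral t distribution, d = 0.5)

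| p | all 80, alpha 0.05 | all 80, alpha 0.005 | targeted participants only, alpha 0.005 |
|---|---|---|---|
| 1.00 | 99% | 94% | 94% (n = 80) |
| 0.75 | 90% | 65% | 83% (n = 60) |
| 0.50 | 57% | 24% | 58% (n = 40) |
| 0.25 | 19% | 4% | 21% (n = 20) |

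Down a column, alpha and the number of tests are constant, so the fall is dilution alone. For 80% power at alpha 0.005 the planned test needs 58 participants at p = 1, 231 at p = 0.50 and 896 at p = 0.25, roughly 58/p². With d = 0.8 and alpha 0.005, the planned and targeted-only tests have 67% and 98% power at p = 0.50, and 12% and 66% at p = 0.25.

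**One score per participant.** Averaging over a participant's own targeted features avoids dilution and keeps everyone with at least one target. If all 80 contribute and d = 0.5, power is 99% at alpha 0.05 and 94% at 0.005.

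**How much of the gain is targeting?** Part of it comes from one test instead of ten. With N = 80, d = 0.6, ten features and between-feature correlation from 0 to 0.5:
- Any of the ten planned tests significant at 0.005: about 31–47% at p = 0.25 and 85–99% at p = 0.50.
- One untargeted mean over all ten features at alpha 0.05: about 43–98% at p = 0.25 and about 95% or more at p = 0.50.

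So an untargeted mean recovers some of the power. The targeted score is equal or higher in nearly all settings.

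**Regression to the mean.** A crossover simulation (N = 80, ten features, about 18–50% of them abnormal, true effect 0.3–0.5 SD, extreme Visit 2 values selected) found that the targeted score held its type I error. It beat the planned family in every non-null setting. For example, power was 97% against 15% (any significant feature) at 18% abnormal, and 68% against 13% at 41% abnormal with noisier measurement.

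**Plausible p.** In a normal reference population 13% of values lie beyond 1.5 SD. The share among these patients is not given.

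**The case against.** **The aim is exploratory, and the responding band may not be known in advance.** Section 3 says outcomes vary with the patterns each brain adopts in response, which is variable response as well as variable targets. Testing all bands is then a defensible screen and a fair check for general or spill-over effects. This stands: the ten tests should be kept, and what is missing is a targeted analysis beside them.

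**Training may span many bands.** A commonly targeted band, perhaps alpha, would be diluted little. This also stands, and is why the size is conditional on p.

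**The power contrast can be exaggerated.** A reader might set 4% for one feature at alpha 0.005 against 99% for one composite at 0.05 and credit the whole gap to dilution. That mixes dilution with a change in alpha and in the number of tests. A reader might also infer that 3A will be null even if training works. Under the assumptions above, at p = 0.50 the planned family usually finds something.

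**The 1.5 SD figure is not a target rule.** A reader might take it as the protocol's definition of what gets trained. It appears inside an example of a normalised outcome. Section 4a gives no threshold for setting goals and does not say that bands within 1.5 SD go untrained.

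**Consequences for the next trial.** Section 7c makes the multicentre trial depend on positive preliminary results and does not tie it to 3A, so the text does not support saying that a null 3A would decide it.

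**Conclusion.** The mismatch is in the text: goals come from individual abnormalities, while the 3A test takes no account of them, and no other planned analysis does. Dilution follows for any feature that was a target in only part of the sample. Under d = 0.5 and alpha 0.05 it takes power for one feature from 99% to 57% at one half targeted and 19% at one quarter. The true loss cannot be fixed from the documents, because p, d and the Bonferroni family are all assumed here, and the calculations also assume no carryover.

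This is a worthwhile, cheap improvement to an exploratory aim. It is not an error that invalidates 3A, and it does not touch the CU outcome.

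**What to change.** In Section 7b:
1. Before treatment starts, record for each participant the features set as training goals at Visit 2. If goals are not recorded by feature, use those with |z| > 1.5 at Visit 2 under a pre-stated rule, including how electrode sites are combined into a feature.
2. Make the main 3A outcome one score per participant and condition: the mean change in |z| over that same fixed feature set in both conditions.
3. Compare active with sham with a period (sequence) term in the model. Selecting extreme Visit 2 values puts regression to the mean into Phase I; balanced order offsets the bias, but the planned paired t-test leaves the period difference in the error.
4. Keep the ten all-band comparisons as supporting analyses of general or spill-over effects, and state their Bonferroni family.

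**Cost.** No new data, since the Visit 2 qEEG is already used to set goals, but the feature rule and the period term must be written into the plan. Participants with no targeted feature drop out of the targeted score. As a rough worst case, with ten independent features each abnormal in 13.4%, 0.866^10 = 24% would have none. The number contributing should be reported.
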